8.10.8. Other Efficacy Analyses

8.10.8.1. Cardiac Hospitalizations

Hospitalization reason will be coded using MedDRA version 19.0. Any adverse event with a preferred term in the broad standardized MedDRA query (SMQ) definition of Cardiac Failure or in the SMQ definition of Cardiac Arrhythmias that results in hospitalization will be counted as a Cardiac Hospitalization.

Time to first cardiac hospitalization admission will be calculated in days as the date of first cardiac hospitalization admission minus the date of first study drug infusion plus 1. Subjects who do not experience an event will be censored at the date of last contact. NEOD001 will be compared to placebo using the same methods described in Section 8.10.7.1. In addition, the time to recurrent cardiac hospitalization, i.e., time to next cardiac hospitalization after the first, will be analyzed in the same manner.

The number of cardiac hospitalizations per subject over the course of the study will be summarized both as a continuous and categorical variable by treatment group. A Poisson regression model will be fit using the continuous number of cardiac hospitalizations as the dependent variable, the total time in study as the offset variable, and treatment group as a factor. The number of cardiac hospitalizations per subject will be categorized as 0, 1, and ≥ 2 . The categorical variable will be analyzed using a CMH test stratified by the randomization stratification factors. The number and percentage, with associated two-sided 95% CIs, of subjects in each category will be presented by treatment group. An ordinal logistic regression

will be performed with categorical number of hospitalizations (0, 1, and ≥ 2) as the dependent variable and factors for treatment group and randomization strata.

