6.4 Vital Status Follow-Up Phone Call

For randomized subjects who received at least 1 dose of study drug, conduct vital status telephone call approximately 3 months after last visit and approximately every 3 months thereafter or until subject enrolls in a separate open-label study, death, or for up to 5 years.

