7 ADVERSE EVENTS/SERIOUS ADVERSE EVENTS AND REPORTING

7.1 Adverse Events—Definition

An AE is any untoward medical occurrence associated with the use of a drug in humans, whether or not considered drug related. An AE can, therefore, be any unfavorable and unintended sign (including a laboratory finding, for example), symptom, syndrome, or disease temporally associated with the use of a medicinal product, whether or not considered related to the medicinal product. Examples include:

- Any treatment-emergent signs and symptoms (events that are marked by a change from the subject's baseline/entry status [e.g., an increase in severity or frequency of preexisting abnormality or disorder])
- All reactions from study drug, abuse of drug, withdrawal phenomena, sensitivity, or toxicity to study drug
- Apparently unrelated illnesses
- Injury or accidents
- Exacerbations of the underlying disease (indication)
- Extensions or exacerbations or symptomatology, subjective events reported by the subject, new clinically significant abnormalities in clinical laboratory, physiological testing, or physical examination

The reporting period for AEs is from the time that the ICF is signed through the last study visit or through 30 days after the last dose of study drug, whichever is later. All AEs, whether or not related to the study drug, must be fully and completely documented on the eCRF and in the subject's medical notes. The following attributes must be assigned: description, dates of onset and resolution, severity, assessment of relatedness to study drug (either related or not related), and action taken. The Investigator may be asked to provide additional follow-up information.

In the event that a subject is withdrawn from the study because of an AE, it must be recorded on the eCRF. The subject should be followed and treated by the Investigator until the AE has resolved, stabilized, or a new chronic baseline has been established.

The Investigator must report all AEs. At each visit the Investigator will ask the subject a nonspecific question (e.g., "Have you noticed anything different since your last visit?") to assess whether any AEs have been experienced since the last report or visit. Adverse events will be identified and documented on the eCRF in appropriate medical terminology. The severity and the relationship to the study drug will be determined and reported on the eCRF ([Sections 7.2 and 7.3](#)).

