4.3. Partial Dates and Unknown Times

If only a partial date is available and is required for calculation, the following standards will be applied:

- Birth Date
 - For missing day only – Day will be imputed as the middle of the month (i.e., 15).
 - For missing day and month – Day and month will be imputed as the middle of the year (i.e., 15 June).
- Death Date
 - The last date that each subject was known to be alive will be identified as the greatest date associated with the subject's completed assessments, including telephone contacts at which the subject was confirmed to be alive.
 - For missing day only – Day will be imputed as the first day of the month (i.e., 1) with the following exception: if the partial date falls in the same month as the last known alive date, then the partial date will be imputed to equal the last known alive date.
 - For missing day and month – Day and month will be imputed as the first day of the year (i.e., 1 January) with the following exception: if the partial date falls in the same year as the last known alive date, then the partial date will be imputed to equal the last known alive date.
- Diagnosis Date
 - For missing day only – Day will be imputed as the first day of the month (i.e., 1).
 - For missing day and month – Day and month will be imputed as the first day of the year (i.e., 1 January).
- Start Dates (e.g., event date, adverse event [AE] onset date, or start date of medication)
 - For missing start day only – Day will be imputed as the first day of the month (i.e., 1) with the following exception: if the partial date falls in the same month and year as the date being used in the calculation (e.g., first infusion date, informed consent date), then the partial date will be imputed to equal the date being used for the calculation.
 - For missing start day and month – Day and month will be imputed as the first day of the year (i.e., 1 January) with the following exception: if the partial date falls in the same year as the date being used in the calculation (e.g., first infusion date, informed consent date), then the partial date will be imputed to equal the date being used for the calculation.
 - Imputed start dates must be prior to the stop date.
- Stop Dates (e.g., AE resolution date or stop date of medication)

- For missing stop day only – Day will be imputed as the last day of the month (i.e., 28, 29, 30, or 31).

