7. STUDY POPULATION

7.1. Subject Disposition

Subject disposition will be tabulated and will include the number of subjects screened, the number screened but not randomized with reasons for screen failure, the number randomized, the number randomized and not treated, the number in each subject population for analysis, the number who withdraw from study prior to completing the study and reason(s) for withdrawal, and the number who discontinued treatment early and reason(s) for discontinuation of treatment.

Time on study in months will be calculated as (last known date of contact minus date of randomization plus one)/30.4375. Time on study drug in months will be calculated as (last infusion date minus first infusion date plus one)/30.4375. KM estimates of the distribution of the time-to-study discontinuation and time-to-treatment discontinuation will be tabulated and graphed by treatment group. The tabulation will include the KM estimate of the medians, 25th and 75th percentiles, and corresponding 95% CIs, if estimable. The tabular and graphical summaries will include the at-risk counts for every visit. In addition, the number and percentage of subjects who complete scheduled visits will be presented. Scheduled visit names will be footnoted to clarify that nominal visits are spaced every 28 days based on study drug infusion occurring every 4 weeks.

The number and percentage of subjects randomized by geographical region and site will be presented by treatment group and overall for the ITT population. The same summary will be presented by calendar year and month.

A summary table will be produced of the IWRS stratification factors and the combined stratum groups:

- Hematologic response; CR/VGPR vs PR to first-line therapy
- Screening NT-proBNP <1800 ng/L vs \geq 1800 ng/L
- Stratum Group 1: CR/VGPR, <1800 ng/L
- Stratum Group 2: CR/VGPR, \geq 1800 ng/L
- Stratum Group 3: PR, <1800 ng/L
- Stratum Group 4: PR, \geq 1800 ng/L

In addition, in case the site accidentally stratified a subject using the wrong stratification value, the derived stratification value reported in the eCRF or central lab data versus the one the site entered in the IWRS during randomization process will be presented separately.

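### Cardiac-hospitalization analyses run follow-up to the last contact, which on its plain reading includes vital-status calls made after adverse-event collection has ended, so unobservable time counts as hospitalization-free

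*SAP*

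**What the plan says.** **Events.** SAP 8.10.8.1 derives a cardiac hospitalization from the adverse-event data: "Any adverse event with a preferred term in the broad standardized MedDRA query (SMQ) definition of Cardiac Failure", or in the Cardiac Arrhythmias SMQ, that results in hospitalization.

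**Follow-up time.** The same section says "Subjects who do not experience an event will be censored at the date of last contact" and applies the same method to time to the next hospitalization. The Poisson model for the count takes "the total time in study as the offset variable". Neither date is defined there. The SAP's only formula of this kind is in 7.1: "Time on study in months will be calculated as (last known date of contact minus date of randomization plus one)/30.4375".

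**When events are collected.** Protocol 7.1 collects adverse events from consent "through the last study visit or through 30 days after the last dose of study drug, whichever is later". Protocol 7.4.4 ends SAE reporting at the same point. A later SAE is passed on only if the Investigator sees a reasonable possibility that the product caused it.

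**What happens afterwards.** For dosed subjects, Protocol 6.4 has sites "conduct vital status telephone call approximately 3 months after last visit and approximately every 3 months thereafter", until open-label entry or death or for up to 5 years. Protocol 4.3 sends subjects who refuse further visits to the same calls. In Protocol Appendix 13, adverse-event assessment appears only in the monthly-visit column. The column for the period after the last visit holds the vital-status call alone.

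**The concern.** A subject can contribute event-free time validly only while an event would have been recorded. If last contact includes the vital-status calls, a heart-failure admission during phone-only follow-up that is judged unrelated to study drug need not reach the database, yet the subject still counts as at risk and event-free. The counted hospitalization rate falls below the true one. If phone-only time differs between arms, the arm with more of it appears to have fewer hospitalizations for that reason alone.

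Entry to the extension study is considered only for subjects who complete this study (Protocol 3.1). Subjects who stop early and also stop attending visits are therefore the likeliest to build up phone-only time.

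**Working it through.** **Step 1. Compare censoring rules within the SAP.**

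| Endpoint (SAP section) | Event-free subjects censored at | Would the event be seen up to that date? |
|---|---|---|
| Overall survival (8.10.7.1) | last assessment known alive | yes; calls capture death |
| Cardiac and renal progression (8.10.7.4) | last NT-proBNP or eGFR assessment | yes |
| Cardiac and renal response (8.10.7.5) | last NT-proBNP, proteinuria or, for the combined endpoint, eGFR assessment | yes |
| Cardiac hospitalization (8.10.8.1) | last contact | not during phone-only follow-up |

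**Step 2. Inputs.** The plan states no rate, event count or power for this endpoint, so it has no figure to reproduce. The stopping rate, hospitalization rate and length of phone follow-up are also absent, so these are assumptions:
- share *s* of an arm with phone-only time after early stopping: 10%, 20% or 30%
- observed time of those subjects: 4 or 7 months
- observed time of everyone else: 12.1 months
- phone-only time *p*: 3, 6 or 12 months
- the same true hazard in both arms

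**Step 3. Dilution of the rate.** With a constant rate, expected events are proportional to observed time, so

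counted rate / true rate = *O* / (*O* + *s* × *p*), where *O* = *s* × (4 or 7) + (1 − *s*) × 12.1.

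Example with 4 months observed and *p* = 6:
- *s* = 30%: *O* = 1.2 + 8.47 = 9.67; 9.67 / (9.67 + 1.8) = 0.843
- *s* = 10%: *O* = 0.4 + 10.89 = 11.29; 11.29 / (11.29 + 0.6) = 0.950
- spurious rate ratio: 0.843 / 0.950 = 0.888, where the truth is 1

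All cases (first figure for 4 months observed, second for 7):

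| Phone-only months | Factor, *s* = 10% | Factor, *s* = 20% | Factor, *s* = 30% | Ratio, 20% vs 10% | Ratio, 30% vs 10% |
|---|---|---|---|---|---|
| 3 | 0.974 / 0.975 | 0.946 / 0.949 | 0.915 / 0.922 | 0.971 / 0.973 | 0.939 / 0.945 |
| 6 | 0.950 / 0.951 | 0.897 / 0.902 | 0.843 / 0.854 | 0.945 / 0.949 | 0.888 / 0.899 |
| 12 | 0.904 / 0.906 | 0.814 / 0.822 | 0.729 / 0.746 | 0.900 / 0.907 | 0.806 / 0.823 |

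**Step 4. Two things that shrink the tilt.** Take the worked example (30% vs 10%, 4 months observed, 6 phone-only months; ratio 0.888).
- Half the stoppers keep attending visits, treated as fully observed. The phone-only shares become 15% and 5%: 10.885 / (10.885 + 0.9) = 0.924 and 11.695 / (11.695 + 0.3) = 0.975, ratio 0.947.
- In addition, 25% of the remaining subjects are phoned for 6 months. The denominators gain 0.25 × 0.85 × 6 = 1.275 and 0.25 × 0.95 × 6 = 1.425, so the factors are 10.885 / 13.06 = 0.833 and 11.695 / 13.42 = 0.871, ratio 0.956. The tilt is smaller, but both rates are understated by more.

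**Step 5. Time to first hospitalization.** An unstratified log-rank simulation used 65 per arm, 4,000 runs, 25% hospitalized by 12 months, stoppers observed for 2-11 months, and equal true hazards.

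| Stoppers | Phone-only months | Median HR, last contact | Median HR, end of collection | False significance favouring the arm with more stoppers, last contact |
|---|---|---|---|---|
| 30% vs 10% | 3 | 0.95 | 1.01 | 3.6% |
| 30% vs 10% | 6 | 0.92 | 1.00 | 4.4% |
| 30% vs 10% | 12 | 0.90 | 0.99 | 5.0% |
| 20% vs 20% | 3, 6, 12 | 1.01, 0.99, 1.00 | 1.01, 0.99, 1.00 | not applicable (equal arms) |

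The nominal one-directional rate is 2.5%. The hazard ratio moves less than the Poisson ratio because phone-only time after the last recorded event adds to person-time but enters no log-rank comparison. With 20% stoppers in both arms, the crude monthly rate falls from about 0.0242 to 0.0230, 0.0218 and 0.0198, that is by about 5%, 10% and 18%, while the hazard ratio stays near 1.

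**The case against.** **Last contact may not mean a phone call.** Section 8.10.8.1 does not define it. The formula in 7.1 belongs to disposition. The wording in 4.3, "including telephone contacts at which the subject was confirmed to be alive", serves the last-known-alive date used to impute death dates. Section 8.10.7.4 dates progression at last contact for subjects whose ETD or EOS form gives progression as the reason for stopping, and a date near discontinuation fits that better. The count is also limited to the course of the study, which Protocol 3.7 ends at the last subject's EOS Visit. The ambiguity is real, so it would be too strong to say the plan expressly counts time to the last call. A call is nevertheless a contact in ordinary language and in 4.3, and nothing in 8.10.8.1 excludes it. Ending at study close would not cure the problem, because a subject who stops early can be phoned for months before the last subject finishes.

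**The early-stopping reading is too strong.** A reader might infer that the arm with more early stoppers must look better. The documents do not support that. Stoppers who continue under Appendix 13 have monthly adverse-event assessment through Month 12, and completers who do not enter the extension are phoned too. What matters is phone-only time, and nothing indicates which arm would have more.

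**Collection does not stop dead at the last visit.** It runs to 30 days after the last dose if that is later, and possibly drug-related SAEs are still reported afterwards. This reduces the unobserved events slightly.

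**Ending follow-up earlier is not a complete cure.** If subjects who leave are sicker, censoring at the end of collection is itself informative. The near-1 hazard ratios in the simulation assume one hazard for everyone.

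**The stakes are limited.** The endpoint is exploratory and outside the gatekeeping sequence. This objection stands.

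**Conclusion.** The concern holds on the plain reading of 8.10.8.1: the follow-up time for the time-to-first, time-to-next and Poisson analyses can extend beyond the period in which hospitalizations are routinely recorded. Rates are then understated wherever phone-only time exists, and the comparison favours whichever arm has more of it.

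The size rests wholly on assumed inputs. Under equal true hazards, the spurious rate ratio is about 0.90-0.97 for 20% versus 10% of subjects with 3-12 phone-only months, and about 0.81-0.94 for 30% versus 10%. It moves towards 1 when stoppers keep attending visits or completers are also phoned. With equal phone-only time in both arms there is no tilt, only rates that are too low.

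The CMH and ordinal analyses of 0, 1 and 2 or more hospitalizations use no follow-up time and are unaffected. The primary and key secondary conclusions are also untouched. This is a correction worth making before unblinding, not a threat to the trial's main result.

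**What to change.** In SAP 8.10.8.1, define one end date for these models: the earliest of death, last contact, and the end of the AE/SAE collection window (the later of last study visit and last dose + 30 days). Censor event-free subjects there, and use time from first infusion to that date as the Poisson follow-up time. The last-contact limit matters because a subject lost soon after a dose should not be credited with up to 30 unobserved days.

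Count only hospitalizations inside that window in these models, and list any later drug-related one separately.

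The cost is a sentence or two of SAP text and one derived date, with no new data. The downside is that late drug-related hospitalizations leave the time-based models.

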3.6 Estimated Study Duration

Each subject's study duration may be up to 14 months, consisting of a Screening Phase (1 month), Treatment Phase (12 months), and the EOS Visit 30 (± 5) days after the last dose.

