2.3.4.8. Other Efficacy Endpoints

2.3.4.8.1. Cardiac Hospitalizations

- Frequency of cardiac hospitalizations over the course of the study

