
Time-to-event data will be summarized using Kaplan-Meier (KM) methodology using 25th, 50th (median), and 75th percentiles with associated 2-sided 95% CIs (where estimable), as well as percentage of censored observations.

All statistical tests comparing groups will be conducted at the 2-sided, 0.05 level of significance, unless otherwise specified. Summary statistics for each treatment group will be presented, as well as two-sided 95% CIs comparing groups will be provided.

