8.10. Exploratory Efficacy Analyses

For applicable exploratory efficacy analyses, if the assumptions of the planned parametric analyses are violated and inhibit the interpretation of the results, appropriate data transformations or parametric analyses will be performed in addition to the other planned sensitivity analyses to support the interpretation of the treatment effect.

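### The Poisson model for cardiac hospitalizations makes no allowance for overdispersion and does not say whether its offset is time or log(time)

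*SAP*

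**What the plan says.** SAP 8.10.8.1 sets out the count model in one sentence. It begins "A Poisson regression model will be fit using the continuous number of cardiac hospitalizations as the dependent variable" and goes on to give "the total time in study as the offset variable, and treatment group as a factor". No link function, time unit, scale parameter, robust variance or dispersion check is stated, and the randomization strata are not in the model.

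The same section counts as a cardiac hospitalization any adverse event that leads to hospitalization and falls in one of two standardized MedDRA queries, cardiac failure or cardiac arrhythmias. It also plans time to first and time to recurrent cardiac hospitalization (by the stratified methods of SAP 8.10.7.1), a stratified CMH test, and an ordinal logistic model with strata. For the last two, "The number of cardiac hospitalizations per subject will be categorized as 0, 1, and" two or more.

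SAP 2.3.4.8.1 lists the endpoint, "Frequency of cardiac hospitalizations over the course of the study", among the exploratory endpoints. SAP 4.1 sets the general test level: "All statistical tests comparing groups will be conducted at the 2-sided, 0.05 level of significance, unless otherwise specified". SAP 8.10 has a general provision for exploratory analyses "if the assumptions of the planned parametric analyses are violated and inhibit the interpretation of the results": transformations or further parametric analyses are then added.

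**The concern.** A Poisson model takes the variance of the counts to equal their mean. Two features of this plan make a larger variance plausible.

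- Subjects differ in cardiac risk. Entry NT-proBNP runs from 650 to 5000 pg/mL, and the SAP's own NYHA subgroups run from class I to III/IV. The plan expects repeat admissions, since it has a category of two or more and a recurrence analysis.
- Events are counted by adverse event. Read literally, a single admission with both a heart-failure term and an arrhythmia term counts twice.

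If the variance does exceed the mean, the model's p-value is too small and its interval too narrow.

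The second issue is the offset. With the usual log link, exposure enters correctly as log(time), so that expected events are proportional to time. The SAP names time itself. A programmer who follows the sentence literally would make expected events proportional to exp(time).

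This is the only planned analysis of hospitalization frequency that adjusts for exposure. The CMH and ordinal analyses ignore length of follow-up, and the time-to-event analyses do not estimate a rate of events. A spurious signal of benefit or harm in this result would therefore be visible, even though it is exploratory.

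**Working it through.** **Inputs from the documents.** Two-sided 0.05 (SAP 4.1); up to 130 subjects randomized 1:1, so 65 per arm (SAP 2.2.5); treatment as the only factor (SAP 8.10.8.1). The plan states no event rate, dispersion, dropout or power for this model, so there is no figure of its own to reproduce.

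**Assumptions.** True rate ratio 1; 0.3 or 0.6 events per subject-year; gamma-distributed subject rates with variance parameter k = 0, 1, 2 or 4; 12 months of full follow-up; early leavers uniform between 1 and 12 months.

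**Step 1: closed form.** With a log link and treatment as the only factor, the Poisson fit gives

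RR = [ΣY₁ / Σexp(o₁)] / [ΣY₀ / Σexp(o₀)], SE(log RR) = √(1/ΣY₁ + 1/ΣY₀),

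where Y is the count and o the offset. The SE does not depend on the offset.

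**Step 2: overdispersion.** If variance = φ × mean, the true SE is √φ times larger, so the actual error rate is about 2[1 − Φ(1.96/√φ)]. With full follow-up, φ = 1 + k × rate. Simulation used 8,000 null trials per case with equal follow-up.

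| φ | 1.96/√φ | Approximation | Simulated |
|---|---|---|---|
| 1.0 | 1.96 | 0.050 | 0.047–0.049 |
| 1.3 | 1.72 | 0.086 | 0.080 |
| 1.6 | 1.55 | 0.121 | 0.110–0.112 |
| 2.2 | 1.32 | 0.186 | 0.179 |
| 3.4 | 1.06 | 0.288 | 0.272 |

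Double counting can do this even with identical subjects. If 30% of admissions carried two qualifying events (an assumption), variance/mean = (0.7 × 1² + 0.3 × 2²)/(0.7 × 1 + 0.3 × 2) = 1.9/1.3 = 1.46. The error rate is then about 2[1 − Φ(1.62)] = 0.105.

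**Step 3: offset read as raw time.** In months, a 12-month subject carries exp(12 − 6) = 403 times the weight of a 6-month subject. The correct factor is 2. Take 30% dropout on NEOD001 and 10% on placebo, with no overdispersion:

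- Mean person-time: 0.7 × 12 + 0.3 × 6.5 = 10.35 and 0.9 × 12 + 0.1 × 6.5 = 11.45 months. The expected event ratio is 10.35/11.45 = 0.904.
- Mean of exp(t) for a leaver: (e¹² − e)/11, about e¹²/11, or 0.091 of a completer's weight.
- Mean weights: 0.7 + 0.3 × 0.091 = 0.727 and 0.9 + 0.1 × 0.091 = 0.909. Their ratio is 0.800.
- RR = 0.904/0.800 = 1.13.

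Simulated medians (6,000 trials per case, 0.6 events per year, k = 0) agree:

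| Dropout, NEOD001 vs placebo | log(time) | months | days | years |
|---|---|---|---|---|
| 30% vs 10% | 1.00 | 1.13 | 1.16 | 0.97 |
| 10% vs 30% | 1.00 | 0.88 | 0.86 | 1.03 |
| 15% vs 20% | 1.00 | 0.97 | 0.97 | 1.01 |
| 20% vs 20% | 1.00 | 1.00 | 1.00 | 1.00 |

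**Step 4: after the change.** With a log(time) offset and a Pearson-scaled SE, the median RR was 1.00 in every case and the error rate 0.044 to 0.060. The negative binomial model was not simulated.

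**Step 5: which time.** SAP 8.10.8.1 does not define total time in study. The nearest definition is in SAP 7.1: "Time on study in months will be calculated as (last known date of contact minus date of randomization plus one)/30.4375". Protocol 3.6 says "Each subject's study duration may be up to 14 months", but vital status calls can continue for up to 5 years (protocol 6.4). Adverse event collection ends 30 days after the last dose or at the last visit, whichever is later (protocol 7.1). If contact by phone counts as time in study, exposure would include periods in which no event is recorded.

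**The case against.** Naming the exposure variable as the offset is common shorthand for log(exposure). Under that reading the rate ratio is unbiased, and a weight factor of 403 is hardly what the authors intended. This stands: the SAP shows an unclear specification, not a decision to use raw time. A reader might infer that the planned rate ratio is wrong whenever follow-up differs. The documents do not support that. Material bias needs both the literal reading and follow-up that differs between arms. It vanishes at 20% dropout in both arms and is small at 15% versus 20%.

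A reader might also infer that the p-values will certainly be too small. That is unsupported too. With no overdispersion the simulated error rate is 0.047 to 0.049, and the documents quantify neither rate nor dispersion. Clustering is plausible, not demonstrated.

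Other analyses of hospitalization are planned, and none uses the Poisson variance or the offset. This also stands and limits the consequence. Omitting the strata does not bias the rate ratio in a randomized comparison, so that is only a matter of consistency within the section.

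The general provision in SAP 8.10 helps less. It names no dispersion check and no substitute model, and it adds analyses to the planned one. An anti-conservative Poisson p-value would still be reported.

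**Conclusion.** The point holds as a low-severity, cheap improvement. The planned model has no protection against overdispersion. If the variance/mean ratio were 1.3 to 2.2, its nominal 0.05 test would have an actual error rate of about 0.08 to 0.18; at a ratio of 1.0 there is no problem. These ratios are assumptions.

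The offset needs clarifying. If it were programmed as raw time, a true ratio of 1 would appear as about 1.13 in months, or 1.16 in days, under an assumed 30% versus 10% dropout. If it means log(time), there is no such bias.

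It would be wrong to conclude that the trial's type I error is at risk. The endpoint is exploratory and lies outside the testing hierarchy of SAP 8.6, and the primary and key secondary tests do not use this model.

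**What to change.** Replace the Poisson sentence in SAP 8.10.8.1 with a negative binomial regression of the number of cardiac hospitalizations per subject, with a log link, log(time at risk) as offset, and factors for treatment group and the randomization strata. Poisson regression with a Pearson-scaled or robust variance, and the same link, offset and factors, is an acceptable alternative and a sensible fallback if the negative binomial fit does not converge.

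Define time at risk as the period over which adverse events are collected, state its unit, and say whether several qualifying adverse events in one admission count once or more than once.

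The cost is a short text change before unblinding, with no new data. Intervals will be wider if the counts are overdispersed.
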